**Sample Size Justification for Aim 1:** We chose our sample size to have sufficient power for both Aims 1 and 2. For Aim 1, the sample size was selected to detect average differences in the primary endpoint (a composite variable indicating either genetic testing or genetic counseling) between the primary randomization arms of interest. The primary comparison groups will be the usual care/waitlist group versus the combined remote telegenetics groups (phone or video conference as one group); the primary analysis will consider the groups prior to the waitlist rerandomization. Preliminary data demonstrated that uptake of genetic testing from an ongoing registered randomized trial of remote telegenetic services vs. usual care for cancer genetic testing in community practices was at least 53% (29/55 with uptake) in the intervention arm, but only 17% (4/24 with uptake) in the control arm. With 120 patients in the usual care/waitlist group and 240 patients in the combined telegenetics groups with complete data (after accounting for loss to follow up), we will have  $>99\%$  power to detect a similar difference in uptake of genetic testing. This assumes a 1% Type I error rate (2-sided) and the use of Fisher's Exact Test. We set the Type I error rate to a conservative 1% to partially account for multiple hypothesis testing when including secondary outcomes and potential moderators in Aim 3. Given the magnitude of the pilot data differences, we anticipate excellent power for the moderator/subgroup analyses. The comparison of the usual care/waitlist group to the combined telegenetics group will be the comparison used to determine if the study accomplishes its primary objective. The uptake of pre-test counseling (Aim 1 secondary objective) and comparison between the phone and videoconference groups (see Aim 2a) are secondary objectives.

**Analyses for Aim 2:** *We hypothesize that remote telegenetic services by videoconferencing will be associated with greater decreases in cancer related distress and depression and increases in knowledge when compared to phone services.* Our primary outcomes for Aim 2a include changes in 1) cancer related distress; 2) depression; and 3) knowledge. We will compare the usual care at baseline group to the combined arms receiving remote services at baseline. For

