To evaluate moderators of patient cognitive, affective and behavioral outcomes (Aim 2b), we will use logistic regressions in which we include variables of interest as covariates. For moderation (i.e. effect modifier analyses), we will include indicator variables for randomization arms in the GEE-estimated multiple linear (for continuous outcomes) or logistic regressions (for uptake); we will also include panel time indicators, the potential moderator variables, and all two-way and three-way interactions among the arm/time/moderator variables. Interactions are created by multiplying two variables together.(82) To maintain power, we will examine non-time moderators separately. We will also examine multiple regression models with potential confounding variables. We will repeat the analyses but assign participants to per-protocol (i.e. restricting sample to those who properly used the method of disclosure as assigned) or as-treated groups (e.g. assigning all participants to a group based on the method of disclosure used, regardless of group assignment).

The economic impact of remote telegenetic services (Aim 2c) will be assessed by performing: 1) cost analysis and 2) cost-effectiveness analysis. The goal of the cost analysis is to estimate the cost of delivering remote telegenetic services, by phone and videoconference, compared to usual care. As above, the cost analysis will take a societal perspective, including the costs of all resources consumed for the implementation and delivery of remote genetic services.

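### High power for the arm effect does not carry over to the moderator analyses: these test interactions, and power for uptake is low unless the interaction is about as large as the main effect

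*Combined protocol and SAP*

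**What the plan says.** The Aim 1 sample size justification in Section 4.0 of the combined protocol and SAP rests on pilot uptake of "at least 53% (29/55 with uptake) in the intervention arm, but only 17% (4/24 with uptake) in the control arm". The sample is described as "With 120 patients in the usual care/waitlist group and 240 patients in the combined telegenetics groups with complete data", and on the test the plan says "This assumes a 1% Type I error rate (2-sided) and the use of Fisher's Exact Test". The stated power for the arm comparison is above 99%. The 1% level was chosen "to partially account for multiple hypothesis testing when including secondary outcomes and potential moderators in Aim 3".

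The plan then adds: "Given the magnitude of the pilot data differences, we anticipate excellent power for the moderator/subgroup analyses". No interaction size, moderator prevalence or moderator power figure accompanies this.

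Further on in Section 4.0, the Aim 2b text defines moderation as effect modification. It is tested by entering arm indicators, time indicators, the moderator, and "all two-way and three-way interactions among the arm/time/moderator variables", in linear models for continuous outcomes and logistic models for uptake.

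**The concern.** The premise and the conclusion concern different quantities. A pilot difference of 53% v 17% gives power to show that telegenetics raises uptake on average. A moderator test asks whether that rise differs between, say, high and low health literacy. The pilot figures give no information on the size of such a difference. Its standard error is also larger: twice that of the main effect on the log-odds scale for an evenly split moderator, and more for an uneven one. Usual care is the limiting arm, with about 20 expected events (0.17 × 120 = 20.4) to divide between moderator levels.

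Aim 2b is a named specific aim. If the protocol records excellent power, a non-significant interaction is easily taken as evidence that the service works equally well across literacy, income or technology-comfort groups. At these sample sizes, a two-fold or three-fold difference in odds ratio would usually be missed.

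**Working it through.** **Inputs from the plan (Section 4.0, Aim 1 sample size):** 240 telegenetics v 120 usual care; uptake 53% (29/55) v 17% (4/24); two-sided 1%; Fisher's exact test for the arm comparison. From the Aim 2b text: logistic model with an arm-by-moderator term for uptake.

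**Assumed, because the plan gives neither:** a binary moderator split 50:50 (20:80 as a variant), usual-care uptake equal at both levels, and a range of interaction sizes.

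**1. The plan's own figure.** Fisher power for 53% v 17% with 240 v 120 at 1% is above 99.99%. The stated figure of above 99% reproduces.

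**2. Standard error of the main effect, log-odds scale.**
SE = √[1/(240 × 0.53 × 0.47) + 1/(120 × 0.17 × 0.83)] = √(0.0167 + 0.0591) = 0.275.
The main-effect odds ratio is (0.53/0.47)/(0.17/0.83) = 5.5. Usual care contributes 0.0591 of the 0.0758 total variance.

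**3. Standard error of the interaction.** For a moderator with prevalence q, approximately SE = 0.275/√[q(1−q)]:
- q = 0.5: 0.275/0.5 = 0.551
- q = 0.2: 0.275/0.4 = 0.688

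**4. Power for a given ratio of odds ratios, q = 0.5.** Power ≈ Φ(ln ratio/0.551 − z), with z = 2.576 at 1% and 1.960 at 5%:

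| Ratio of odds ratios | Power at 1% | Power at 5% |
|---|---|---|
| 2 | 9% | 24% |
| 3 | 28% | 51% |

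**5. Ratio needed for 80% power at 1%.** exp[(2.576 + 0.842) × SE] = 6.6 for q = 0.5 and 10.5 for q = 0.2. Both exceed the main-effect odds ratio of 5.5.

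**6. Interaction expressed as a share of the main effect.** Here the pilot fractions are used unrounded (difference 36.1 points), usual-care uptake is 16.7% in both halves, the average effect is held fixed, and the Wald test is on the log-odds scale with variances taken at the stratum rates:

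| Interaction | Arm effect in the two halves (points) | Power at 1% | Power at 5% |
|---|---|---|---|
| 0.5 × main effect (18 points) | 27 v 45 | 10% | 26% |
| 1.0 × (36 points) | 18 v 54 | 55% | 77% |
| 1.5 × (54 points) | 9 v 63 | 95% | 99% |

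A likelihood-ratio simulation (4,000 runs) gave 11%, 54% and 91% at 1% for the same rows.

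**7. Arm effect within one subgroup.** Fisher's test at 1%, with the same arm difference:

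| Subgroup | Usual care v telegenetics | Power |
|---|---|---|
| Half | 60 v 120 | 99% |
| Quarter | 30 v 60 | 77% |
| Fifth | 24 v 48 | 63% |
| Tenth | 12 v 24 | 21% |

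**The case against.** The strongest reply is that the plan gives no interaction size or moderator split, so any low power figure rests on assumed values. That stands. A reader might infer that the sample simply has very low power for moderation. The documents do not support this as an unconditional statement: with an interaction 1.5 times the main effect, power at 1% exceeds 90%. That case, however, requires a benefit of 9 points in one half and 63 in the other, and nothing in the plan suggests variation of that order.

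Second, the sentence covers subgroup as well as moderator analyses, and for the arm effect within half the sample it is correct. This also stands, but the claim weakens quickly in smaller subgroups.

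Third, the scale matters. On the risk-difference scale, power at 1% for a 50:50 moderator is 26%, 64% and 92% for interactions of 0.5, 0.75 and 1.0 times the main effect, and 80% power needs about 31 points. This is a fair qualification, but the planned model for uptake is logistic.

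Fourth, no confirmatory conclusion depends on the sentence, and the plan nowhere says that a null interaction will be read as a uniform effect. Both are true, and they are why this is a correction to wording and interpretation rather than to the design.

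A reader might also infer that any significant moderators would be mostly false positives. The documents do not support that. The plan says only that the 1% level is meant to "partially account for multiple hypothesis testing when including secondary outcomes and potential moderators in Aim 3", so it does not claim full control. For 11 to 16 moderators on the primary composite, treated as independent, the chance of at least one false positive is 1 − 0.99^11 = 10% to 1 − 0.99^16 = 15%. The share of significant results that would be false depends on how many real interactions exist, which is unknown.

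**Conclusion.** The claim of excellent power for the moderator analyses does not follow from the reason given. For uptake under the planned logistic model, power at 1% stays low until the interaction is about as large as the main effect, and it is only about 55% at that point. These figures rest on 240 v 120, pilot uptake of 53% v 17%, an evenly split binary moderator and equal usual-care uptake at both levels. An uneven split raises the detectable ratio (10.5 at 20:80). The claim holds for the arm effect within roughly half-sample subgroups and not for markedly smaller ones. The plan's calculation for the primary comparison is correct and is unaffected. The figures here concern uptake and do not address the continuous Aim 2b outcomes.

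**What to change.** Replace the sentence with a statement along these lines: power is high for the arm effect within subgroups of about half the sample, but low for effect modification unless the interaction is about as large as the main effect or larger. Give the detectable interaction with its assumptions, for example a ratio of odds ratios of about 6.6 for 80% power at 1%, with a 50:50 moderator and 17% usual-care uptake at both levels.

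Label the Aim 2b moderator analyses exploratory. Report interaction estimates with confidence intervals, and state that a non-significant interaction will not be read as evidence of a uniform effect.

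While editing, reconcile the reference to moderators under Aim 3 in the Aim 1 sample size text with their placement under Aim 2b in Sections 2.0, 3.3 and 4.0.

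The cost is wording and a less favourable stated power. Sample size, data collection and the primary analysis do not change.

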### 3. Genetic Testing

**ARMS A and B:** If patients on Arms A and B elect to proceed with genetic testing, they will be asked to provide their PCP's/ or other provider's (usual source of care or a local health care provider of their choice) contact information. A licensed physician is required to order genetic testing in most states. If [name] or [name] has licensure in the residing state, they will be the ordering physician if no PCP/ provider has been identified. The Penn Telegenetics Team will contact the patient's PCP/provider and their practice to inform them that their patient is a candidate for remote genetic services and the Penn Telegenetic counselors can provide counseling and facilitate testing through a collaborative relationship with the patient's provider. The PCP/provider would need to agree to be the ordering provider for the genetic testing and register with the Penn Telegenetics Program, a model that has been successful in our current clinical program. PCPs/providers will provide their credentials and contact information, so that the GC can collaborate with the provider to facilitate testing. Practice staff will be permitted to complete the PCP/provider registration on behalf of the provider. Once the PCP/provider has registered and agreed to support testing in their patient, the Penn GC will collaborate with the patient and provider/practice to arrange for sample collection, and provide support for insurance coverage. The registered PCP/provider will receive a chart note summarizing the pre-test counseling visit and testing ordered.

**ARM C:** Participants in the usual care arm will receive usual care services depending on which referral method they choose and if they initiate services. As below, after the 6-Month Outcome Survey, if they have not had genetic services through usual care they will be offered services and re-randomized to Arm A/B in a waitlist design.

**Genetic Testing in all arms** will be clinical cancer genetic testing through standard clinical commercial labs, consistent with real-world practice and as indicated based on their personal

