#### 4. Genetic Testing Result Disclosure, Visit 2 (Remote Telegenetics Arms)

**ARM A: Remote telegenetic counseling by videoconference:** The Penn GC will share results with the patient by videoconference at a scheduled visit. The Penn GC will provide the patient's provider with a chart note, summarizing the results and associated implications and cancer risk estimates, as well as standard risk reducing or screening strategies and implications for relatives. Penn GCs will be available to answer PCP/provider questions (by email or phone) and facilitate referral to regional clinical expertise centers as indicated. Patients will be recommended to follow-up with their PCP/provider to implement any screening and medical (including risk reduction) recommendations. If the participant consents, this session will be recorded for research and training purposes.

**ARM B: Remote telegenetic counseling by phone:** The Penn GC will share results with the patient by phone at a scheduled visit. The remainder of procedures for post-test counseling are as described above for Arm A. If the participant consents, this session will be recorded for research and training purposes.

Following the completion of the disclosure session, participants on Arms A and B will also be asked to complete a study survey (T2) (**Appendix H**).

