#### 5. Completion of Primary Outcome 6-Month Status Survey (Usual Care Arm & Certain Remote Telegenetics Arms Participants, **Appendix I1**)

Participants on the usual care arm will be contacted at the 6-month timepoint (6-months post randomization) to assess uptake of genetic services. Participants on Arms A and B that have not completed genetic counseling or testing will also be contacted at the 6-month timepoint to assess uptake of genetic services through the 6-Month Status Survey. Those who have had genetic testing will be asked to provide authorization for the study team to obtain a copy of their genetic test result for the purpose of research (**Appendix I2**).

Participants on Arm C that have not had genetic testing at 6 months will be offered telegenetic services (waitlist design, see **Study Schema**). This option will not be shared at enrollment. Rather, they will be told that after they complete the 6-Month Status Survey, we will review again genetic testing options with them.

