## OUTCOMES AND MEASURES

Table 1. Effectiveness outcomes and measures			
CONSTRUCT	T0	T1	T2-T4
Moderators of patient outcomes			
Sociodemographics	X		
Cancer history	X		
Family history	X		
Health literacy	X		
Comfort with technology	X		
Self-efficacy	X		
Financial Wellness	X		
COVID Impact	X		X
Outcomes			
Uptake counseling, testing, identification carriers at 6 months* (Telegenetics records for Arms A/B & the 6-Month Status Survey in Arm C)			
Understanding of Genetic Information**			
Test result recall			X
Knowledge of genetic disease	X	X	X
Perceived risk	X	X	X
Reactions to genetic information**			
Anxiety and Depression	X	X	X
Cancer specific distress	X	X	X
Satisfaction with genetic services and telemedicine		X	X
Behavioral use of genetic information**			
Performance of behaviors	X		X
Cost (patient and system)**		X	X

\*Aim 1; \*\*Aim 2; T0=baseline (within 30 days of visit 1, can accept within 45 days. beyond that it needs to be updated), waitlist usual care participants will need to complete a new baseline, T0b; T1=survey post pre-test counseling, Visit 1 (ideally collect 1-3 days and up to 7 days. accept up to 14 days but from 7-14 days we may elect to drop and impute). T2=survey immediately post genetic testing disclosure (same timing as T1); T3/T4 survey=6/12-month post genetic testing disclosure (ideally get within 14 days of 6/12 month mark but accept within 60 days of 6 month or 12 month mark)

The T0-T4 patient surveys for the RCT will be completed through a secure website, linked through the myLTFU platform. The 6-Month Outcome Survey will be administered by phone. If the phone survey cannot be completed, the survey will be offered self-administered through the myLTFU platform.

Effectiveness Outcomes (Aims 1 and 2):

**1) Uptake of counseling, testing and identification of carriers at 6 months** (Aim 1): This information will be obtained through study records for Arms A and B (intervention arms) and the 6-Month Outcome Survey among nonresponders in Arm A and B (e.g. those who did not contact Penn Telegenetics or did not complete visit 1 or visit 2) and in Arm C (usual care). The outcome survey will query completion of each outcome, date, and provider and will explore barriers and reasons for no uptake (Appendix I).

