comparisons between the remote videoconferencing versus phone groups, we will assign participants to the remote group assigned at baseline, or after rerandomization for the waitlist group. Our primary change scores for the first three variables will be change between baseline and immediately post genetic testing. For the waitlist group, there will be a second baseline measurement after the usual care period has ended. For the 3 primary analyses in Aim 2, we will use T-tests. We will assess balance of potential confounders (e.g. age, race, study site, waitlist assignment) between arms using T-tests or Fisher's exact tests as appropriate. Waitlist group will be considered a confounder in these secondary regression analyses. We will use multiple linear regression models to control for potential confounders inadequately balanced. We will include in the models the confounding variables and indicator (binary 0/1 variables) to indicate randomization arms (leaving one group out as the reference). For longitudinal analyses, we will examine time trajectories using regressions estimated by Generalized Estimating Equations (GEE) to account for within subject temporal correlation. Panel time will be included via indicator variables. We will also include interaction terms between randomization arm and time indicators to investigate temporal effects.(82) We will repeat analyses, but assign participants to per-protocol (i.e. restricting sample to those who properly used the assigned method of disclosure) or as-treated groups (e.g. assigning all participants to a group based on the method of disclosure used, regardless of assignment). For Aim 2 secondary outcomes, we will use multiple linear regressions for continuous outcomes and multiple logistic regressions for binary outcomes using GEE-estimation as described.

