### **5.1 Payment to subjects:**

Participants will receive a gift card code in the defined amount for the completion of the following surveys in the randomized trial:

- Baseline (T0) Survey: \$25
- Pre-Test Counseling Session Session (T1) Survey (Arms A & B): \$25
- Disclosure Counseling Session (T2) Survey (Arms A & B): \$25
- 6-Month Follow Up (T3) Survey (Arms A & B): \$30
- 6-Month Outcome Survey (Arm C only): \$75
- 12-Month Follow Up (T4) Survey (Arms A & B): \$30

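### The usual-care v combined-remote sentence under Aim 2 names no outcome or time point and cannot be run on the Aim 2a change scores; some users of services outside the study also have no listed cost survey for the three-arm ICER

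*Combined protocol and SAP*

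**What the plan says.** **Aim 2a comparison.** Section 4.0 (Analyses for Aim 2) lists the Aim 2a primary outcomes as changes in cancer-related distress, depression and knowledge. It continues: "We will compare the usual care at baseline group to the combined arms receiving remote services at baseline". It then turns to videoconference v phone, where "we will assign participants to the remote group assigned at baseline, or after rerandomization for the waitlist group". One change score is defined: "Our primary change scores for the first three variables will be change between baseline and immediately post genetic testing". That end point is T2 in the footnote to Table 1.

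**Who has T2.** Section 3.3, item 4: "Following the completion of the disclosure session, participants on Arms A and B will also be asked to complete a study survey (T2". The outcomes text in Section 3.3 measures understanding of, and reactions to, genetic information at T0 in all arms but at T1 to T4 only in Arms A and B. Section 5.1 lists payment for the "Disclosure Counseling Session (T2) Survey (Arms A & B".

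**T0b.** The Table 1 footnote says "waitlist usual care participants will need to complete a new baseline, T0b". Section 4.0 likewise calls it a second baseline, taken once the usual-care period is over.

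**Costs.** Section 2.0 promises incremental cost-effectiveness for all three arms (Aim 2c). Section 4.0 puts patient time and travel in the ICER numerator. The cost paragraph of Section 3.3 takes these from participant surveys and, like Table 1, schedules cost collection at T1 to T4. Items 6 and 7 of Section 3.3 give T3 and T4 to everyone who has been tested; Section 5.1 lists payment for them in Arms A and B only.

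**The concern.** A stated comparison should have an outcome, a time point and data in both groups. Placed where it is, the usual-care sentence reads as an analysis of the Aim 2a change scores, for which Arm C has no end point. An analyst following the text would have to drop it, choose another time point, or use only those Arm C participants who enter the waitlist. No rule is given for that choice, and the contrast has no stated power and no stated place in the three-outcome Bonferroni correction.

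For the ICER, patient costs would be collected unevenly. Participants who use services outside the study's own telegenetic visits, in any arm, are the ones most likely to lack a cost survey. Entering their costs as zero shifts the numerator.

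**Working it through.** **1. What the plan powers.** Table 2 was reproduced first, using the change-score differences and SDs printed there, SD = √((s₁² + s₂²)/2), two-sided alpha 0.05/3 = 1.67%, power 85% and a two-sample t-test.

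- Knowledge: difference 18.6 − 5.7 = 12.9, SD 11.92, gives 22 per arm (plan: 22).
- Distress: difference 3.6 + 2.6 = 6.2, SD 12.35, gives 95 per arm (plan: 95).
- Depression: difference 1.6 − 0.2 = 1.4, SD 2.0, gives 50 per arm (plan: 50).

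All three agree, and all three are phone v videoconference. No sample size is given for usual care v remote on these outcomes.

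**2. Measurements by group before re-randomization.**

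| | Arms A and B | Arm C |
|---|---|---|
| T0 | yes | yes |
| T1, T2 | yes | no |
| 6-Month Outcome Survey | non-completers | yes |
| T0b | no | waitlist entrants only, after the usual-care period |

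A T0-to-T2 change therefore exists for 0 of 120 in Arm C. A T2 obtained after re-randomization belongs to the video or phone group under Section 4.0's own assignment rule. The GEE trajectory models do not help, because Arm C has no T1 to T4 panel in this period.

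**3. Whether T0b fills the gap.** It does not. The plan treats it as a new starting point, Arms A and B have no matching measurement, and it is limited to waitlist entrants, a group defined by what happened after randomization. Entry is also worded two ways: "Participants on Arm C that have not had genetic testing at 6 months will be offered telegenetic services" (Section 3.3, item 5), against "if they have not had genetic services through usual care they will be offered services and re-randomized to Arm A/B in a waitlist design" (item 3). A participant counselled but not tested meets the item 5 condition and not the item 3 condition. That is a separate drafting matter to be reconciled.

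**4. Whether an Arm C T2 would repair it.** At the pilot uptake rates in the Aim 1 sample size text, 120 × 4/24 = 20 in Arm C and 240 × 29/55 = 126.5, about 127, in Arms A and B would be tested. The contrast would set two self-selected groups against each other. These are planning figures; the June 2023 amendment note now expects 60 to 80 visit 2 completers per remote arm.

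**5. Cost surveys by type of user.**

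- Usual care, counselled but not tested: T1 and T2 belong to Arms A and B, and T3 and T4 follow testing. None listed.
- Arms A and B, outside counselling without testing: T1 follows the study's own visit 1, and T2 to T4 follow disclosure. None listed.
- Usual care, tested: T3 and T4 under items 6 and 7 of Section 3.3, but not in the Section 5.1 payment list.

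The 6-Month Outcome Survey is described as covering completion, date, provider, barriers and reasons for no uptake. No cost item is mentioned.

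**6. Direction and scale.** ICER = (cost remote − cost usual care) / (proportion tested remote − proportion tested usual care). Omitting usual-care patient costs raises the numerator, against remote services. Omitting outside-service costs in Arms A and B lowers it, in their favour.

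For scale on the first term only, assume the rates of the earlier community-practice trial in Section 1.0 carry over: 6% counselled in usual care; 61% v 17% tested. Each $1 of uncollected cost per counselled usual-care user then moves the cost per additional survivor tested by 0.06/(0.61 − 0.17) = $0.14. With the Aim 1 pilot testing rates in the denominator it is 0.06/(0.527 − 0.167) = $0.17. The documents give no rate of outside use in Arms A and B, so the opposing term, and hence the net, cannot be computed.

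**The case against.** The strongest reply is that the sentence was never meant for the Aim 2a change scores. Section 2.0 defines Aim 2a as videoconference v phone, and the Aim 2 hypothesis, Table 2 and the Bonferroni correction all follow that definition. The sentence names no outcome and is followed at once by an assignment rule for video v phone, so the two may be a pair of grouping rules. Aims 2b and 2c do need usual-care contrasts, on uptake and cost, and Arm C has uptake data. The sentence could also be left over from Aim 1. All of this stands. A reader might infer that the plan firmly commits to an impossible Aim 2a analysis; the documents do not support that. They support only that outcome and time point are unstated and that the reading suggested by the sentence's position cannot be carried out. It also follows that simply deleting the sentence could remove a rule that is needed.

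On costs, a reader might infer that no usual-care patient costs are collected, or that the ICER is biased against remote services. Neither is established. Appendix I1 is listed but was not available, and the cost paragraph is expressly about usual care as well as remote services. Section 5.1 is a weak guide to who is surveyed: it assigns the 6-Month Outcome Survey to Arm C alone, although Section 3.3 also gives it to Arm A/B non-completers. The Arm A/B restriction in the outcomes text covers understanding and reactions, not cost. What stands is that the stated cost timepoints omit the 6-Month Outcome Survey and miss counselled-only users outside the study's visits.

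**Conclusion.** The point holds as a minor one, in two parts.

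First, the usual-care v combined-remote sentence lacks an outcome and a time point. On the Aim 2a change scores it has no Arm C data before re-randomization (0 of 120 by schedule), and T0b is not a substitute.

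Second, the listed cost timepoints leave usual-care participants who are counselled but not tested, and Arm A/B participants who use outside services without testing, with no cost survey. The plan is also unclear on whether tested usual-care participants receive T3 and T4. The resulting biases in the ICER oppose each other, and the net is unknown and probably modest. The $0.14 to $0.17 per $1 describes one side only and assumes that rates from other trial populations apply. The second part is in part a query, since Appendix I1 may already hold the items.

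Nothing here touches the Aim 1 primary analysis or the powered video v phone tests, and a reader should not infer that it does.

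**What to change.** 1. Reword the Section 4.0 sentence so that usual care v combined remote is limited to outcomes Arm C has (uptake and cost). State that the Aim 2a change scores are compared for video v phone only. If a T0-to-T0b summary in waitlist entrants is wanted, label it descriptive and place it outside the three primary tests.
2. Reconcile items 6 and 7 of Section 3.3 with the outcomes text and Section 5.1 on who receives T3 and T4.
3. Unless Appendix I1 already has them, add time, travel, out-of-pocket and service-use items to the 6-Month Outcome Survey for Arm C and Arm A/B non-completers, and name that survey as a cost timepoint in the cost paragraph of Section 3.3. If those surveys are already complete, vary usual-care patient cost per user over a stated range in the sensitivity analysis Section 4.0 already plans.

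The cost is one reworded sentence, aligned statements of the T3/T4 population, and at most a few items on a survey already being given. The downsides are slight participant burden and a difference in recall and mode (a six-month phone survey against web surveys near the visit), to be reported as a limitation. If Appendix I1 already holds the items, there is no added burden.
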